### **Interventions**

**Combined home-based exercise group.** Participants in this group will exercise throughout their chemotherapy treatments, starting within 1-2 weeks of its start and ending within 3-4 weeks post-treatment completion .

The exercise intervention will be led by qualified exercise professionals, comprising two weekly 60-minute online exercise group sessions with a 5-minute warm-

up, a 30-minute resistance training, and a 20-minute aerobic exercise component, finishing with a 5-minute cooldown . The warm-up will be composed of mobility and activation movements, such as cat-camels, butterfly chest stretch, overhead reach, floor angels, spine twist in sitting and alternated all fours position, doorway chest stretch, wall slides, scissors, pointer, and single leg stances. The resistance training component will consist of 9 different exercises, performed either with body weight or free weights, completing 2-3 sets of 10-15 repetitions, and will involve movements such as chair sit-to-stand, multi-directional lunges, calf, and toe raises, double-arm and one-arm rows, push-ups, glute bridges, clams, chest press, multi-directional shoulder raises, leg curls, and abdominal exercises (i.e., crunches, leg raises, crisscross) . The aerobic component will consist of low-impact dance exercises, moving large muscle groups to increase heart rate, involving marching, side steps, knee raises, leg curls, multi-directional arm movements, and dance movements . The cooldown will consist of breathing exercises and light stretches. Every exercise professional will follow a written protocol to ensure consistency in the intervention program's application .

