Before the beginning of the exercise program, participants will receive an education session on how to use Borg's Perceived Rate of Exertion Scale (RPE) to monitor their effort during aerobic and resistance training and tips on when they may increase the exercise intensity . During the training sessions, participants in the intervention group will be asked to choose their preferred load to execute each exercise in the resistance component, told to perform the aerobic exercises at their preferred speed, and informed that they can stop exercising whenever they need to rest. The exercise professional may suggest increasing loads in specific exercises, but these increases will not be imposed on the participants. Attendance to the sessions in the intervention and control groups will be registered. Additionally, women in this group will be encouraged to perform brisk walking at their preferred intensity and receive a pedometer to increase walking motivation .

**Control group.** Women randomized to the control group will receive weekly 30-minute supervised sessions with breathing, stretching, relaxation exercises, and meditation during the intervention period . Women in this group will not be forbidden to perform PA but will not receive any incentives or advice from the supervising exercise professional.

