### **Plans to promote retention**

The conducting exercise professional will control participants' adherence to the exercise program through a presence registry collected by the research team member with access to the list of participants' numbers. After the session, the non-interventionist research team member will pass the presence list to the respective numbers of the participants for program adherence analysis. If a participant fails to attend a session, contact will be made to ensure the participant's welfare and motivate them to participate

in the next session. The data analysis will not consider participants who fail to attend 50% or more sessions. Positive feedback will be given to the participants during the sessions, as positive feedback is proven to enhance feelings of competence, enjoyment, and interest in the activity . Additionally, participants will be encouraged to keep an activity diary where they may register all activities performed autonomously. Participants will be contacted one week before the assessment to confirm their availability and presence. Data from participants who fail to perform the assessments during the intervention period will be excluded from data analysis. After the intervention, participants will be contacted monthly to check their well-being and keep their interest and motivation in engaging in the follow-up assessment.

\*\*\* Table 2\*\*\*

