### **Statistical methods**

All data will be analyzed using IBM SPSS (version 29.0). Factorial ANCOVAs with repeated measures will be used for the primary and secondary outcomes, adjusted for potential covariates (e.g., concomitant treatments, BC diagnosis, neo-adjuvant/adjuvant chemotherapy). Independent sample T-tests will be used to compare results between groups at each time point, considering chemotherapy completers versus non-completers . A Fisher's exact test will compare the proportion of participants who needed chemotherapy adjustments from those who did not . The intention-to-treat analysis will be conducted to ensure that all participants are included in the overall assessment, considering their compliance with the study protocol. The Last Observation

Carried Forward method will be used to input missing data values. A per-protocol analysis will also be conducted without participants who failed to complete at least 50% of the training sessions. Normality plots and Kolmogorov-Smirnov tests will be performed to test the normality of outcome variables. If normality is not satisfied, non-parametric tests will be applied (e.g., Krustal-Wallis). Mediators of change (i.e., mechanisms by which RDI) will be explored using structural equation modeling (AMOS 18.0) and multiple mediation analysis (PROCESS macro for SPSS). Putative candidates will include treatment (e.g., dose planned vs. given dose, planned cycles minimum/maximum, treatment interruption ratios, response to treatment, percentage of participants who needed dose adjustments, and the mean value of dose adjustment), and physiological (e.g., body composition, functional performance, handgrip strength, PA levels) variables. Mediation occurs when a causal effect of an independent variable occurs on a dependent variable, partly or entirely explained by a mediator. Indirect effects testing will be performed using Preacher and Hayes' procedures.

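### Excluding women by session attendance takes the RDI comparison outside the protection of randomisation, and the resulting bias may plausibly favour exercise

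*Protocol*

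**What the plan says.** Statistical methods plans two analyses. One keeps everyone: "The intention-to-treat analysis will be conducted to ensure that all participants are included in the overall assessment". The other removes low attenders: "A per-protocol analysis will also be conducted without participants who failed to complete at least 50% of the training sessions". No adjustment is planned for the reasons sessions were missed, and the text does not say how the rule applies to controls.

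Plans to promote retention repeats the exclusion without limiting it to a per-protocol set: "The data analysis will not consider participants who fail to attend 50% or more sessions".

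The sessions being counted differ by arm. Under Interventions, the exercise arm has "two weekly 60-minute online exercise group sessions", made up of resistance and aerobic work. Controls have "weekly 30-minute supervised sessions with breathing, stretching, relaxation exercises, and meditation". Attendance is recorded for both: "Attendance to the sessions in the intervention and control groups will be registered".

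Under Primary outcome, RDI is obtained from medical records, so it can be known for a woman who attended no sessions.

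**The concern.** A per-protocol comparison is only as good as the comparability of the women left in it. Here the selection variable shares a probable cause with the outcome. The Background lists fatigue, sickness and pain among the reasons women do not keep active. The discontinuation criteria ask women whose worsening condition makes exercise unsafe to stop. The same toxicity can lead to chemotherapy delays and dose reductions, which lower RDI. Removing low attenders therefore tends to remove women with low RDI.

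If this happened equally in both arms, the difference between arms would be unaffected when there is no true effect. The two kinds of session make equality doubtful: an unwell woman may manage half an hour of breathing and relaxation when she cannot manage an hour of exercise. The exercise arm could then lose more of its low-RDI women, and its mean would rise without any benefit.

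The Background reports earlier trials with no effect of exercise on RDI. A null result in all women beside a more favourable one among attenders is therefore a realistic outcome, and it could be misread as support for Hypothesis 1. The general exclusion under Plans to promote retention could carry the same selection into the main analysis.

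**Working it through.** The Protocol gives no attendance rate, expected per-protocol size, RDI mean or RDI standard deviation, so there is no stated figure to reproduce. All inputs below are assumptions, apart from the 98 women from Sample size, the 1:1 allocation from Trial design and the 85% cut-off from Primary outcome.

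**1. Arithmetic check with two toxicity classes and no true effect.** Assume 40% of women have high toxicity (RDI 80) and 60% low toxicity (RDI 95). With everyone kept, both arms average 0.4 × 80 + 0.6 × 95 = 89.0.

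- Exercise keeps 50% of high-toxicity and 90% of low-toxicity women: (0.4 × 0.5 × 80 + 0.6 × 0.9 × 95) / (0.20 + 0.54) = 67.3 / 0.74 = 90.95.
- Control keeps 80% and 95%: (0.4 × 0.8 × 80 + 0.6 × 0.95 × 95) / (0.32 + 0.57) = 79.75 / 0.89 = 89.61.
- Spurious difference: 90.95 − 89.61 = +1.34 points.
- Same retention pattern in both arms: 0. Patterns swapped between arms: −1.34. Retention unrelated to toxicity (70% v 90% overall): 0.

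**2. Continuous model with no true effect.** RDI = min(100, 92 − 6U + e), where U ~ N(0,1) is toxicity and e ~ N(0, SD 7). The resulting RDI standard deviation is about 7.7. The probability of meeting the 50% rule is 1 / (1 + exp(−(a − bU))), where b is the strength of the link from toxicity to attendance. Controls have a = 2.0. Entries are exercise minus control in mean RDI points.

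| Exercise a, b (share kept) | Control b = 0.3 (88% kept) | Control b = 1.0 (84% kept) | Only exercise arm filtered |
|---|---|---|---|
| 1.0, 1.0 (70%) | +1.10 | +0.58 | +1.29 |
| 1.0, 1.5 (67%) | +1.63 | +1.10 | +1.81 |
| 1.2, 1.0 (73%) | +0.96 | +0.43 | +1.15 |
| 1.2, 1.5 (70%) | +1.48 | +0.96 | +1.66 |

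The share with RDI of at least 85% shifts by +1.8 to +6.9 percentage points with both arms filtered, and by +4.8 to +7.6 with only the exercise arm filtered.

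**3. Patterns that remove or reverse the shift in the same model.**

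- Same a and b in both arms: 0.
- Exercise a = 1.2, b = 1.0 (73% kept) against control a = 2.0, b = 1.5 (81% kept): about 0.
- Exercise a = 1.2, b = 0.3 (76% kept) against control a = 2.0, b = 1.0 (84% kept): −0.35, although exercise still loses more women.

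The sign depends on how strongly toxicity drives absence in each arm as well as on how many women each arm loses.

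**4. Scale against sampling error.** With 98 / 2 = 49 per arm, SD 7.7 and 70% and 87% retained, the standard error of the difference is √(7.7² / 34.3 + 7.7² / 42.6) ≈ 1.8 points. A second model (RDI mean 92, SD 10, capped at 100, correlation 0.6 with toxicity; attendance correlated 0.5 with low toxicity) gives, at 41 to 49 per arm:

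- 30% v 10% excluded (exercise v control): +0.7 points, false-positive rate about 7% instead of 5%.
- 30% v 0%: +1.2 points, about 10%.
- Strongest case tried (attendance correlation 0.7, 40% v 0%): +2.2 points, 21% to 24%.
- 10% v 30%: −0.7 points.

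**The case against.** The strongest reply concerns direction. A reader might infer that the 50% rule is certainly harder to meet in the exercise arm and so certainly favours exercise. The documents do not support that certainty. The rule is a proportion, so two sessions a week rather than one does not by itself raise the bar. The Background describes home-based exercise as having high adherence, the programme is to be shaped by participants' preferences, load and pace are self-selected, and women may rest when they wish. With no attendance figures, zero or reversed bias cannot be excluded. This part of the objection stands, and the direction is only plausible.

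A reader might also infer that only the exercise arm is filtered, because training sessions in the ordinary sense exist only there. That reading is strained. Attendance is registered in both groups, Strategies to improve adherence says control-group adherence will be considered, and the retention section speaks of participants and sessions without naming an arm. The larger range is therefore a secondary scenario.

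Finally, the per-protocol analysis is additional to intention-to-treat, and nothing says it will be used to confirm Hypothesis 1. By Statistical methods alone it does not carry the main conclusion. But the Protocol does not rank it below intention-to-treat either, and the unrestricted exclusion under Plans to promote retention leaves the main analysis exposed. The exclusion rule is a stated choice, so this is not a detail merely awaiting an SAP.

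**Conclusion.** The concern holds in a limited form. Selecting on attendance forfeits the protection of randomisation, and the Protocol itself supplies both the probable link from illness to absence and the unequal sessions. Under the assumed inputs and no true effect, the shift is roughly 0.5 to 1.6 RDI points with both arms filtered (+0.43 to +1.63, or about 0.06 to 0.21 SD). It is about 1.2 to 1.8 points if only the exercise arm is filtered. These are modest shifts against a standard error near 1.8 points, and they vanish or change sign under other equally assumed patterns. What is established is that the comparison is unprotected and may be biased, plausibly towards exercise. A certain direction or a known size is not established. The change is worth making because it is cheap and because the general exclusion could otherwise reach the primary result.

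**What to change.** 1. State that the conclusion on Hypothesis 1 rests on all randomised women, analysed as randomised, with RDI taken from medical records whatever their attendance.
2. Reconcile the attendance exclusion under Plans to promote retention with this, either by deleting it or by limiting it to the per-protocol analysis.
3. State that the attendance-exclusion analysis is descriptive and does not support Hypothesis 1. Say how the 50% rule applies in each arm: which sessions count, and out of how many.
4. If an effect of adherence is wanted, add a randomisation-based instrumental-variable estimate that keeps all randomised women, with exercise attendance either as a continuous exposure or as a 50% threshold. The threshold version is the intention-to-treat difference divided by the share of exercisers meeting the rule. State the exclusion restriction: assignment affects RDI only through the exposure as defined. It is doubtful here, because exercisers below 50% still attend some sessions and also receive a pedometer and walking encouragement. In one illustrative simulation with benefit proportional to attendance, the threshold estimate was 3.48 against a true 2.85 among compliers (3.48 / 2.85 = 1.22, or 22% too high). A continuous exposure deals with partial attendance but not with the pedometer or walking advice.

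The cost is a few sentences of wording and a short analysis of data already being collected. The instrumental-variable estimate brings a wider interval and that extra assumption.

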## **Objectives**

This study will investigate the effects of a structured, supervised, home-based combined exercise intervention with self-selected intensity on the chemotherapy completion rates of women with BC. We also intend to analyze the impact of this intervention on functional performance, body composition, PA levels, and quality of life. A 3-month follow-up will be performed to investigate short-term outcomes and active lifestyle sustainability post-intervention.

Hypothesis 1: Women in the intervention will have a better completion rate than those in the control group.

Hypothesis 2: Women in the intervention will present better functional performance, body composition, PA levels, and quality of life than the control group.

Hypothesis 3: In the post-intervention period, women in the intervention group will maintain a more physically active lifestyle than women in the control group.

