### **Sample size**

Considering this study design, sample size calculations were made for the primary outcome with a factorial variance analysis with repeated measures as reference statistical analysis, giving an initial estimation of 82 participants. Based on previous findings and considering a 20% dropout, the sample size was estimated at 98 participants with a moderate effect size ( $\alpha=0.05$ ; statistical power=0.80) according to Cohen's D calculations, using G\* Power 3.1 .

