### **Assignment of interventions**

#### **Allocation**

##### **Sequence generation**

After signing the informed consent form, participants will be given a number, randomly generated through Excel and emailed by a non-interventionist team member, which will be their participant number throughout the study. Participants will be instructed not to reveal their number to the research team or the other participants and to keep it with them until the end of the study. After all baseline assessments, participants will be randomly assigned to either the intervention or control arm through an online program (<https://www.graphpad.com/quickcalcs/randomize1/>). If recruitment takes longer than expected, adjustments in allocation may be made.

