### **Primary outcome**

**Chemotherapy completion rates.** Chemotherapy completion rates will be assessed at  $T_0$ ,  $T_1$ , and  $T_2$ . This outcome will be reported as the mean RDI ( $\text{mg} \cdot \text{m}^{-2} / \text{wk}^{-1}$ ), which corresponds to a fraction of the planned chemotherapy dose intensity, by dividing the dose of chemotherapy per square meter (of surface area where the drug is related) in each cycle by the number of weeks in a cycle . Information regarding the planned chemotherapy treatment and the effectively received treatment (i.e., dose, type, and duration) will be acquired from medical records after signing the informed consent . A successful chemotherapy completion rate will be considered if the RDI is  $\geq 85\%$  of the planned treatment, as an RDI below this cut-off is associated with a worse disease prognosis and lower treatment efficacy . Calculations to compare the actual chemotherapy dose intensity received and the initially planned dose intensity will be calculated as total milligrams of chemotherapy divided by the product of the body surface (in square meters) and total weeks of treatment . The RDI results from the actual dose intensity received are divided by the planned dose intensity .

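### A normality test on the raw outcome can replace the adjusted primary analysis with a non-parametric test, and the only one named gives no adjusted difference in mean RDI

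*Protocol*

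**What the plan says.** Protocol, Statistical methods, sets the model: "Factorial ANCOVAs with repeated measures will be used for the primary and secondary outcomes, adjusted for potential covariates". Later in the same section comes the check: "Normality plots and Kolmogorov-Smirnov tests will be performed to test the normality of outcome variables". The consequence follows directly: "If normality is not satisfied, non-parametric tests will be applied (e.g., Krustal-Wallis".

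The rule covers outcome variables without restriction, so the primary outcome falls under it. The section also plans independent-sample t-tests at each time point and a Fisher's exact test. It does not say whether the ANCOVA, the t-tests or both give way.

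On the primary outcome, the Primary outcome section says "This outcome will be reported as the mean RDI", with RDI assessed at T0, T1 and T2, and describes it as a quantity "which corresponds to a fraction of the planned chemotherapy dose intensity". The Sample size section says "sample size calculations were made for the primary outcome with a factorial variance analysis with repeated measures as reference statistical analysis", which gives 82 women, or 98 after a 20% dropout allowance. The claim at stake is "Hypothesis 1: Women in the intervention will have a better completion rate than those in the control group".

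**The concern.** Three things do not fit together.

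- **The object of the check.** The ANCOVA assumes normal residuals. The protocol tests the outcome itself, whose shape also reflects covariates and arm.
- **The fallback.** With two arms, Kruskal-Wallis is equivalent to the Mann-Whitney test. It has no time factor, no covariates and no estimate on the RDI scale.
- **The likelihood of the switch.** A fraction of planned dose may pile up near 100%, which is a shape that a normality test rejects.

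At stake is what the trial reports for Hypothesis 1. The planned analysis estimates an adjusted difference in mean RDI. If the rule fires and the named test is used, that estimate is no longer the primary result.

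**Working it through.** **1. The plan's own sample size.** The protocol calls the effect moderate and gives no number, so Cohen's f = 0.25 is assumed, with two groups, alpha 0.05, power 0.80 and correlation rho = 0.5 between measurements. For the group effect in a repeated-measures ANOVA, lambda = f² × N × m / (1 + (m − 1) × rho), with 1 and N − 2 degrees of freedom. With m = 4 and N = 82, lambda = 0.0625 × 82 × 4 / (1 + 3 × 0.5) = 20.5 / 2.5 = 8.2. The smallest N reaching 80% power is 82, so the stated figure is reproduced. With m = 1 the same formula needs 128. The planned size therefore leans on repeated measurements, which a one-value test discards.

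**2. What is planned against what the named fallback provides.**

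| Feature | Planned analysis | Kruskal-Wallis |
|---|---|---|
| Measurements per woman | several | one |
| Covariates | yes | none |
| Quantity compared | mean RDI | ranks |
| Adjusted difference in mean RDI | yes | no |

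**3. How often the check would fire.** The protocol gives no RDI distribution, so every shape here is an assumption. A share p of women has RDI exactly 100%; the rest have RDI = 1 − Beta(1.5, b). There are 2,000 replicates per scenario (Monte Carlo standard error at 5%: √(0.05 × 0.95 / 2000) ≈ 0.5 points). Share of data sets in which Kolmogorov-Smirnov rejects at 0.05:

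| Women tested | Version | p = 0 | p = 20% | p = 40% |
|---|---|---|---|---|
| 98 pooled | Lilliefors | 91.9% | 99.7% | 100% |
| 98 pooled | uncorrected | 24.2% | 71.7% | 100% |
| 82 pooled | Lilliefors | 82.0% | 99.2% | 100% |
| 82 pooled | uncorrected | 15.7% | 50.4% | 100% |
| 49, one arm | Lilliefors | 61.0% | 84.2% | 100% |
| 49, one arm | uncorrected | 4.1% | 7.3% | 84.7% |

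With normal data, the Lilliefors version rejects in about 4 to 5%.

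**4. Raw outcome against residuals.** With normal errors, 82 women and a binary covariate shifting the mean by 1.5, 2, 2.5 or 3 SD, the raw outcome is rejected in 3.6%, 5.0%, 14% and 37% of data sets, and the residuals in 3.3 to 4.0%. The wrong object matters only when a covariate effect is large.

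**5. False positives.** The adjusted comparison is represented by the group effect over T1 and T2 with one covariate and HC3 robust standard errors. Over the null shapes tried it rejects in 3.8 to 5.9%; Kruskal-Wallis at T2 rejects in 3.3 to 4.2%. The full two-stage procedure (test normality, then choose) gave about 4 to 5% in one run and 4.7 to 6.8% in another, where HC3 without the pre-test gave 3.7 to 6.5%.

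**6. Power, 49 per arm.** Mean loss among women below 100% is 1.5 / (1.5 + b), so b = 6, 8.5 and 13.5 give 20%, 15% and 10%.

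| Assumed effect | Adjusted model | Kruskal-Wallis at T2 |
|---|---|---|
| 20% vs 40% at 100% RDI (b = 8.5) | 33% | 40% |
| 40% vs 60% at 100% RDI (b = 8.5) | 36% | 44% |
| 10% at 100%; mean loss 15% vs 10% | 74% | 49% |
| 40% at 100%; mean loss 20% vs 10% | 85% | 32% |

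This contrast combines three changes: loss of T1, loss of the covariate, and ranks instead of means. It cannot be attributed to ranks alone.

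**The case against.** **The fallback is only an example, and the analysis it replaces is not named.** This stands in part. Kruskal-Wallis is a natural substitute for the t-tests, and the wording leaves other non-parametric methods open. A reader might infer that the protocol orders Kruskal-Wallis in place of the ANCOVA; it does not say that. But it exempts no outcome and names no rank method that handles repeated measures or covariates. The rule is also stated as something that will happen, so it is not a detail merely left to a statistical analysis plan.

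**Two analysts would reach different verdicts.** A reader might infer this from the unspecified test version. The adjusted model and Kruskal-Wallis do give different verdicts in 18 to 54% of data sets under the four assumed effects, but that compares always using one with always using the other. When the pre-test is actually run pooled, and analysts differ only in the Kolmogorov-Smirnov version, verdicts differ in 0 to 2% of data sets, and in 15% in one scenario. Where 40% or more of women are at the ceiling, both versions reject and both analysts take the same branch. Differences from reading the plots were not quantified.

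**No error inflation.** This stands. A pre-test on pooled data is not an arm comparison, and the Blinding section says that the analysis is done blinded.

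**The rank comparison was made at T2 only.** This stands as a limit. Kruskal-Wallis on the mean of T1 and T2 had more power in all four scenarios, for example 60% instead of 50%, and 41% instead of 30%.

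**Mean RDI by arm can still be tabulated.** True. What is lost is the covariate-adjusted difference with its interval.

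**Conclusion.** The concern holds as a defect in a stated rule. A normality check on the outcome variables can move the primary analysis to an unspecified non-parametric test, and the only one named does not estimate the quantity the protocol says it will report. Under the assumed shapes with 98 pooled women, the Lilliefors version fires in 92 to 100% of data sets. The uncorrected version ranges from 24% with no ceiling to 100% with 40% of women at it. If arms are checked separately with the uncorrected version, switching is rare unless many women sit at 100%.

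A reader might go further and infer inflated false positives or a certain loss of power. Neither is supported. The two-stage procedure stays near 5% in the null shapes, and the rank test gains power in two of the four effect scenarios and loses it in the other two. The structural mismatch follows from the text alone; every rate rests on assumed RDI distributions, correlations and effects. The rule should be changed, but the case is about what gets estimated, not about an invalid test.

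**What to change.** In Statistical methods, remove the normality rule for the primary outcome and state that:

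- the pre-stated covariate-adjusted repeated-measures comparison of the arms is the primary analysis whatever the normality result;
- diagnostics are done on model residuals, not on raw outcomes;
- inference within that model uses robust standard errors, a bootstrap or a permutation test, with one chosen in advance;
- the result is the adjusted difference in mean RDI with its 95% confidence interval;
- any rank-based test is a sensitivity analysis only.

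The cost is an edit to the wording and slightly more analysis work, with no new data. The real downside is that in some shapes, such as arms differing mainly in the share of women at 100% RDI, a rank test would have had somewhat more power (40% against 33%, or 44% against 36%, in the scenarios above).

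### Several treatment-type candidate mediators are components of RDI itself, so with RDI as the mediated outcome that part of the mediation analysis is circular

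*Protocol*

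**What the plan says.** The Primary outcome section of the protocol defines dose intensity as "calculated as total milligrams of chemotherapy divided by the product of the body surface (in square meters) and total weeks of treatment", and then states: "The RDI results from the actual dose intensity received are divided by the planned dose intensity". Of the completion rate it says: "This outcome will be reported as the mean RDI".

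The Statistical methods section introduces the mediation analysis as follows: "Mediators of change (i.e., mechanisms by which RDI) will be explored using structural equation modeling (AMOS 18.0) and multiple mediation analysis". The parenthesis breaks off before saying what RDI does or what is mediated.

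Two families of candidates follow. The treatment family contains "dose planned vs. given dose, planned cycles minimum/maximum, treatment interruption ratios, response to treatment, percentage of participants who needed dose adjustments" and the average size of dose adjustment. The second family is "physiological (e.g., body composition, functional performance, handgrip strength, PA levels) variables". The section also gives its own definition: "Mediation occurs when a causal effect of an independent variable occurs on a dependent variable, partly or entirely explained by a mediator".

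The Abstract announces the mediation analysis, and the Dissemination policy commits to publishing it.

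**The concern.** A mediator has to be a separate variable that the intervention changes and that in turn changes the outcome. A term in the formula for the outcome does not qualify. Given-versus-planned dose is the dose part of RDI, the mean dose adjustment and the need for adjustment restate that part, and interruptions lengthen the weeks in the denominator.

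Two things are at stake. A result for these variables would look like near-complete mediation but would say only that RDI is made of dose and time. And if they share a model with the physiological candidates, an exercise mechanism that really operates through fitness or body composition could be reported as absent, because it can reach RDI only through dose and time.

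**Working it through.** The protocol states no figure for this analysis, so there is none to reproduce. The check is algebra from the Primary outcome definitions, followed by a simulation for illustration.

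**1. The identity.** For one drug, with the same body surface (BSA) in the received and planned terms:

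- received intensity = mg given / (BSA × actual weeks)
- planned intensity = mg planned / (BSA × planned weeks)
- RDI = (mg given / mg planned) ÷ (actual weeks / planned weeks) = dose ratio / duration ratio
- log RDI = log(dose ratio) − log(duration ratio)

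Example with assumed values: dose ratio 0.93 and duration ratio 1.05 give RDI = 0.93 / 1.05 = 0.886. On the log scale, −0.0726 − 0.0488 = −0.1214, and exp(−0.1214) = 0.886.

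A regression of log RDI on arm and the two log ratios must therefore return coefficients of +1 and −1 and an arm (direct) effect of 0, whatever the biology. In least squares, total = direct + indirect, so the indirect effect equals the total.

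**2. The listed items against the formula.**

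| Listed item | Relation to RDI |
|---|---|
| Planned versus given dose | The dose ratio itself |
| Mean dose adjustment; need for adjustment | Restate the dose term |
| Treatment interruption ratios | Feed the weeks term (measure not defined) |
| Planned cycles | Part of the planned regimen; the intervention is unlikely to move it |
| Response to treatment | Not in the formula; plausibly follows dose delivery |
| Body composition, function, handgrip, PA | Not in the formula |

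**3. Simulation on the raw scale.** Inputs: n = 98 from the Sample size section ("the sample size was estimated at 98 participants with a moderate effect size"), 49 per arm, 4000 replicates. The Abstract gives a recruitment goal of 122, but the identity does not depend on n. The distributions are assumptions: dose ratio centred near 0.93 and capped at 1, duration ratio centred near 1.05 with a floor of 1, both driven by a latent tolerance score.

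| Assumed arm shift in tolerance | Total | Direct | Indirect | R² |
|---|---|---|---|---|
| 0.5 SD | 0.0283 | 0.0001 | 0.0281 | 0.998 |
| None | 0.0007 | 0.0000 | 0.0007 | 0.998 |

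The mediated share in the first row is 0.0281 / 0.0283 = 99%. In the second row the total is only simulation noise, yet the indirect effect still reproduces it.

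**4. Masking.** A second simulation let fitness act on RDI through both dose and duration, with the arm raising fitness by 0.5 SD (assumed).

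| Mediators in the model | Indirect effect through fitness | Share of the total, 0.0210 |
|---|---|---|
| Fitness alone | 0.0207 | 0.0207 / 0.0210 = 99% |
| Fitness, dose ratio and duration ratio | 0.0001 | 0.0001 / 0.0210 = 0.5% |

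The same true mechanism is recovered in the first model and lost in the second.

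**5. Timing.** Dose intensity uses total milligrams and total weeks, so RDI at T2 is cumulative and includes doses given before T1. A change from T0 to T1 does not fully precede it; it does precede RDI accrued between T1 and T2.

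**The case against.** The strongest reply is that the mediation analysis as a whole is not circular. A reader might infer that it can show no mechanism at all. The document does not support that: the physiological candidates stand in the same sentence, are not parts of RDI, and are recoverable when modelled without its components. This stands.

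Masking also requires a joint model. The reference to multiple mediation allows one but does not fix it, and model composition may be left to an analysis plan that is not shown. So masking is a risk and not a certainty. The circular items are different: the protocol itself names them as candidates.

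RDI as the dependent variable is an inference from an incomplete sentence. If RDI were instead a mediator of, say, quality of life, its components would be collinear with it, but the outcome would not be built from them and the figure of about 100% would not apply. This stands as a condition on the conclusion.

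The simulation builds RDI from the two ratios, so its near-total mediation follows from the definition. That is a fair description, and it is also the point being made. But the figure needs both terms to be captured. The duration ratio is not listed as such, and interruption ratios need not equal it, so a model holding only some of the items could show a smaller share. That share would still be a decomposition of RDI.

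A reader might also infer that a percentage of participants cannot be used as a mediator because it has no value for an individual. The same section plans a Fisher's exact test on whether participants needed adjustment, so a yes/no value for each woman exists and the percentage is most naturally loose wording for it. The remaining objection to that item is its overlap with RDI.

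**Conclusion.** The point holds for the delivery variables: planned versus given dose, mean dose adjustment, need for adjustment, and interruption ratios. With RDI as the mediated outcome they fail the protocol's own definition of mediation. The dose and duration ratios together account for about 100% of any arm difference, exactly so on the log scale.

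This rests on RDI being the outcome and on one body surface value being used in both terms. If RDI is averaged over several drugs, the identity is exact for each drug and approximate for the average. The masking result (0.0207 falling to 0.0001) rests on the assumed simulation inputs and on a joint model.

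Response to treatment and planned cycles are unsuitable for separate reasons: the first by time order, the second because it is probably set before the intervention can act. The physiological part remains sound if kept apart from the RDI components. The analysis is exploratory, and the primary comparison and the sample size are unaffected. The change should still be made before analysis, because the mediation results are promised for publication.

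**What to change.** In Statistical methods:

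1. Complete the unfinished sentence so that it names the mediated outcome.
2. Remove the delivery variables, planned cycles and response to treatment from the mediator set.
3. Report the delivery variables by arm as a descriptive decomposition of RDI into dose and time, with need for dose adjustment recorded as yes/no for each woman.
4. Keep functional performance, handgrip strength, body composition and PA as mediators, measured as change from T0 to T1, and relate them to RDI accrued from T1 to T2 instead of cumulative RDI at T2. State how a woman whose chemotherapy ends before T1 is counted.

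The cost is a wording change. No new data are needed, because doses and durations already come from the medical records. The mediator list becomes shorter. RDI after T1 covers only the later part of treatment, so it is less precise than the primary measure. Early dose delivery may also affect fitness at T1, so the estimates remain exploratory.
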